10. ADVERSE EVENTS

Adverse event (AE):

Any untoward medical occurrence in a patient or clinical trial subject administered a pharmaceutical product or device and which does not necessarily have to have a causal relationship with this treatment.

An AE can be any unfavorable and unintended sign (including an abnormal laboratory finding, for example), symptom or disease temporally associated with the use of a medicinal product, whether or not considered related to the medicinal product or device.

The intensity (severity) of a specific event, as perceived by the patient, is typically described as mild, moderate or severe (although a severe event itself may be of minor medical significance). The term serious is based on the event outcome or action criteria usually associated with events that pose a threat to a participant's life or functioning. Seriousness serves as a guide for defining regulatory reporting obligation.

Serious Adverse Event (SAE):

A serious adverse event (experience) is any untoward medical occurrence that at any dose:

1. results in death,
2. is life-threatening,
3. requires inpatient hospitalization or prolongation of existing hospitalization,
4. results in persistent or significant disability/incapacity

It should be noted that the term "life-threatening" in the definition of "serious" refers to an event in which the patient was at risk of death at the time of the event. It does not refer to an event that hypothetically might cause death if it were more severe.

Medical and scientific judgment should be exercised in deciding whether expedited reporting is appropriate in other situations. These include important medical events that may not be immediately life threatening or result in death or hospitalization but may jeopardize the patient or may require intervention to prevent one of the other outcomes listed in the definition above. These should also usually be considered serious.

Unexpected adverse event:

An unexpected AE is defined as "any adverse event, the specificity or severity of which is not consistent with the current investigator's brochure; or, if an investigator brochure isn't required or available, the specificity or severity of which is not consistent with the risk information described in the general investigational plan or

elsewhere in the current application, as amended" (adopted from ICH E6 guideline, "Good Clinical Practice: Consolidated Guideline").

10.1 Recording of Adverse Events

Adverse events will be recorded for all subjects who receive the study device. Adverse events will be documented in subject diaries, during in-clinic assessments, and during telephone contacts through Contact 3 (Day 730) of the study. All adverse events will be graded by severity and relationship to the experimental device and followed until resolution or the completion of subject participation. All SAEs will be recorded throughout the 2 year period of safety surveillance.

Any subject who was discontinued due to an AE or non-adherence to the protocol windows for study agent administration will be followed for safety and efficacy endpoints by clinic visits, telephone contacts, and subject diaries as specified by the protocol. All safety evaluations will continue to be completed according to the protocol, if possible.

All AEs that are moderate or mild will be submitted within 7 days from the site to the designated Medical Monitor, [name].

10.2 Reporting of Serious Adverse Events

During the study period all SAEs must be reported to the sponsor immediately (within 24 hours). Any SAE occurring from the time of device placement until termination of the study, whether deemed device-related or not, must be reported by facsimile to Agenta immediately (usually within 24 hours) using a SAE Report Form.

SAE Contact Information (Agenta Medical Monitor):

[name].

Cell Phone (24 hours): [contact]

FAX (24 hours): [contact]

Additional contact information for the Medical Monitor is provided in Section 1 of this protocol, "Study Contacts."

The SAE Report must include the Investigator's written medical judgment as to the relation of the event to the experimental device (i.e., "definite/certain", "probable", "possible" or "unrelated"). This initial judgment can be modified later by the investigator, as more information relevant to the SAE becomes available.

Definite/Certain Related is applied to those SAEs which have a temporal relation to the study device and no alternative etiology is present. It must have occurred within a reasonable temporal sequence of the device administration (0 - 7 days), must not be reasonably explained, and must follow a known pattern of response.

Probable Related has a timely relation to the study device and a potential alternative etiology is not apparent (e.g., fever or malaise when no other symptoms suggestive of an illness are present).

Possible Related has a timely relation to the study device; however, a potential alternative etiology exists which may be responsible for the symptom (e.g., fever or malaise when other symptoms are present that suggest another etiology such as urinary tract infection).

Unrelated is applied to those SAEs where evidence exists that the event is definitely related to an etiology other than the study device (e.g., auto accident, or a symptom suggestive of another illness, which is not accepted to be a possible event due to the experimental device).

Participants will be instructed to call the study site to report SAEs at any time during the study period through 24 months. In addition, active surveillance of SAEs will be performed at every scheduled site visit or telephone call. In the event that a study participant reports a SAE, study personnel will be authorized to visit or telephone the participant until the problem is resolved. Any SAE is to be documented and fully described whether or not it is consider to be related to the study device.

A report of any SAE must be followed by a written report to the IRB, the SRC and to Agenta, by the Investigator, including a full description of the event and any sequelae. All deaths, whether considered device-related or not, must also be reported immediately to the IRB, the SRB, and to Agenta.

Agenta will report all SAEs to the government agencies, adhering to timelines for reporting outlined in Therapeutic Products Program Directorate Guidelines (ICH/GCP) and the Code of Federal Regulations (21CFR 312.32). The FDA will be notified of any SAE as soon as possible, not later than 15 days, and within 7 days for any death or life-threatening event associated with the drug substance (experimental device).

All SAEs must also be recorded in the appropriate section of the CRF. All reported SAEs will be reviewed periodically by the SRC.

11. TRIAL ASSESSMENTS

11.1 Safety

The safety profile to be assessed includes immediate adverse events, solicited local and systemic events, unsolicited adverse events, and hematologic and biochemical toxicity evaluation.

11.1.1 Immediate Adverse Events

All participants will be observed for 30 minutes after administration of the study treatment. Any immediate AE will be recorded on the AEs page.

11.1.2 Solicited Local and Systemic Events

All subjects will be given diary cards that are to be filled out for the purposes of recording any changes in health status after device administration.

- Diary Card #1 will be used to record all local and systemic events, as well as any other AEs that represent a change in the health status of the subject, from device placement through Visit 3 (Day 7).
- Diary Card #2 will be used to record unsolicited adverse events and SAEs through Visit 4 (Day 42).
- Diary Card #3 will be used to record unsolicited adverse events and SAEs after Visit 4 (Day 42) through Visit 5 (Day 180).
- Diary Card #4 will be used to record unsolicited adverse events and SAEs after Visit 5 (Day 180) through Visit 6 (Day 360).
- Diary Card #5 will be used to record unsolicited adverse events and SAEs after Visit 5 (Day 360) through Contact #3 (Day 720).

The diary cards will be considered the source document and will be transcribed into the case report form (CRF) by study site personnel. If the diary card is lost, this will be documented in the CRF, and the limited information collected during the clinic visit will serve as the source document. All other data points will be noted with "ND" (not determined).

For the purpose of collecting solicited local and systemic events, the following procedures will be implemented:

1. Study participants will be supplied with a digital thermometer on day 7 and shown how to use it to measure their oral temperature for weeks 1-6 following administration of the study product.
2. Participants will be asked to observe for AEs daily during the first 6 weeks post-implantation period. This includes systemic events including fever, chills, nausea/vomiting, weakness, muscle pain, and headache.
3. Diary Card #1 will be distributed during Visit 1 (Day 0) and collected during Visit 3 (Day 7). Diary Card #2 will be distributed during Visit 3 (Day 7) and collected during Visit 4 (Day 42). Diary Card #3 will be distributed during Visit 4 (Day 42) and collected during Visit 5 (Day 180). Diary Card #4 will be distributed during Visit 5 (Day 180) and collected during Visit 6 (Day 360). Diary Card #5 will be distributed during Visit 6 (Day 360) and collected by mail at Contact #3 (Day 720). Subjects will be asked

to bring their current diary card to each clinic visit. At each visit, the study staff will review with the participant the information found in the diary card for clarity and completeness but will not make changes to the subject’s information. However, the participant may add to or amend the information on the card if appropriate. Any information crossed out by the participant should be deleted with a single strikethrough line in order to maintain the legibility of the original information, and should be initialed and dated by the participant. For any questions not completed, the participant should record “ND” (not determined) beside the question.

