3. SCHEDULE OF EVALUATIONS

Visit Number	Screen	Visit 1	Contacts 1 and 2	Visit 2	Visit 3	Visit 4	Visit 5	Visit 6	Contact 3
Trial Timeline	Day -21 to 0	Day 0	Days 1 and 2 ¹	Day 3	Day 7	Day 42	Day 180 ¹	Day 360 ¹	Days 720 ¹
Visit/Contact Window (Days)	N/A	N/A	+/- 0	+/- 1	+/- 1	+/- 4	+/- 28	+/- 28	+/- 28
Informed Consent	X								
Inclusion/Exclusion	X	X							
Medical History	X								
Interim Medical History		X	X	X	X	X	X	X	X
Concomitant Medications	X	X	X	X	X	X	X	X	
Physical Examination	X								
HIV and Illicit Drug Test	X								
Physical Assessment: Vital Signs ² /Node Check		X		X	X	X	X	X	
Safety Labs (CBC, Blood Chemistry, PT, PTT, Urinalysis) ^{2,3}	X	X			X	X			
Surgical Treatment		X							
Surveillance (30 minutes)		X							
CT	X	X				X	X	X	
Diary Cards Distributed/Collected		X			X	X	X	X	X
Unsolicited Adverse Events		X	X	X	X	X	X	X	X

¹ Subjects will be contacted at Days 1 and 2, Days 42 and at 6 months, 1 year, and 2 years with a scripted telephone contact for safety follow-up and scheduling.

² Vital signs and laboratory values will be evaluated using the appropriate FDA draft guidance.

³ Any abnormal laboratory result arising post-administration, and of moderate or greater severity, will be followed until results return to baseline value or for the duration of safety follow-up.

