- d. Verify telephone contact information and mailing address and provide instructions to participant in the event of a change in contact information.

Additional Clinic Visits

Any subject with an abnormal laboratory result or who experiences an adverse event may be requested to come into the clinic for additional follow-up evaluation not specified by the protocol if this is deemed medically prudent by the investigator.

9.2 *Obtaining, Handling, Storage, and Shipment of Specimens*

9.2.1 *Blood Samples for Safety Laboratory Tests*

Blood samples collected for safety analysis will be labeled and handled per the local reference laboratory standard operating procedures for hematology and biochemistry profiles. Blood samples for safety laboratory tests will include one 5 mL and one 10 mL sample, as well as one 4 mL sample for PT and PTT testing where specified.

9.2.2 *Urine Samples*

A clean-catch urine sample will be collected by each participant for safety evaluation. Study personnel will be responsible for instructing subjects on this technique. Urine samples will be handled and labeled per the local reference laboratory standard operating procedures for urinalysis.

9.3 *Safety Data Review*

The SRC will perform a review of the safety data through seven days post-administration for the first three subjects, and through seven days post-administration for all subsequent subjects. The SRC will use the following evaluation criteria to approve the completion of enrollment after the first 3 subjects:

- a) Absence of SAEs or severe AEs "definitely", "probably" or "possibly" related to the experimental device.
- b) No evidence of severe hematologic or biochemical toxicity.
- c) No consistent pattern of AEs that, in the judgment of the SRC, represents a significant threat to the safety of the subjects with continued enrollment.

Approval from Agenta will be obtained before proceeding with treatment of subjects 4-12.

9.4 *Compliance with Protocol*

All participants who receive the experimental device will be included in the safety evaluation.

The following events are to be considered sufficient reason for discontinuation of a participant from the study:

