11.1.4 Adverse Event Grading Scales

The severity of all adverse events will be graded as mild (Grade 1), moderate (Grade 2), severe (Grade 3), or potentially life threatening (Grade 4) according to the adverse event grading scale provided below. This grading scale will be used for local adverse events (those related to the cranial site of device administration) and systemic adverse events.

Mild (Grade 1)	Moderate (Grade 2)	Severe (Grade 3)	Potentially Life Threatening (Grade 4)
Symptom is present but does not interfere with activity	Symptom interferes with some activities but does not cause missed attendance at school or work	Incapacitating, unable to attend school or work or perform essential daily activities	Requires emergency room visit or hospitalization

Abnormal vital signs will be graded according to the above severity scale. This grading scale is based on the scale provided in the draft FDA guidance for industry, “Toxicity Grading Scale for Healthy Adult and Adolescent Volunteers Enrolled in Preventive Vaccine Clinical Trials” (April 2005).”

Any "severe" rating for local or systemic events requires the participant to call the study site for evaluation, the study site to notify the Medical Monitor (at the discretion of the investigator), and place comments on the AE page of the CRF that describe the event(s). Any severe adverse event that is deemed possibly, probably or definitely related to the study treatment will invoke a temporary stopping rule for the study to permit evaluation of the event by the SRC (see Section 14.3).

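### Section 11.1.2 hands out the thermometer on Day 7 for temperatures meant to cover weeks 1-6, just as the only card for local and systemic events is collected

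*Protocol*

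**What the plan says.** Section 11.1.2, item 1, fixes the hand-out day: "Study participants will be supplied with a digital thermometer on day 7 and shown how to use it to measure their oral temperature". The same sentence gives the period to be covered: "oral temperature for weeks 1-6 following administration of the study product". Item 2 asks participants to look for adverse events every day for six weeks and adds: "This includes systemic events including fever, chills, nausea/vomiting, weakness, muscle pain, and headache".

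The card descriptions in the same section divide the recording. For the period from placement to Day 7, "Diary Card #1 will be used to record all local and systemic events". Item 3 has that card collected at Visit 3 (Day 7). For the next period, "Diary Card #2 will be used to record unsolicited adverse events and SAEs through Visit 4 (Day 42". Cards #3 to #5 are also described as taking unsolicited events and SAEs.

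Other sections give different periods for solicited events: one year on diary cards (synopsis), daily for two years (Section 7.1), and rates analysed through Day 360 ± 28 days (Section 13.2.1).

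On grading, Section 11.1.4 says: "Abnormal vital signs will be graded according to the above severity scale". Footnote 2 to the schedule in Section 3 says: "Vital signs and laboratory values will be evaluated using the appropriate FDA draft guidance".

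**The concern.** A thermometer that arrives on Day 7 cannot produce readings for week 1, so item 1 cannot be carried out as written. The instrument also reaches the participant at the visit where the card for systemic events is taken back, and the card that replaces it is described as being for something else.

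Two uses of the data are affected. First, the Safety Review Committee decides whether to open enrolment after reviewing data "through seven days post-administration for the first three subjects" (Section 9.3). This is a 12-subject study of a plasmid product for which Section 5.5 reports no previous human experience with this approach, and safety is the primary objective. A named solicited sign should have a specified measurement in that week. Second, Section 13.2.1 reports solicited and unsolicited rates separately. If the card decides the label, a fever on Day 5 counts as solicited and the same fever on Day 20 counts as unsolicited.

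**Working it through.** The protocol states no figure for this, so the check is a day count and a comparison of sections.

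**Inputs.** Weeks 1-6 are taken as Days 1-42. The thermometer is supplied and Card #1 collected at Visit 3, Day 7 with a window of ±1 day (Section 3). Card #2 runs from Visit 3 to Visit 4. Scheduled vital signs after surgery in week 1 are on Days 3 and 7 (Sections 3 and 9.1).

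**Thermometer and card coverage.** With Visit 3 on day w, thermometer days = 42 − w + 1, days without = w − 1, overlap with Card #1 = 1 (day w itself), and thermometer days under Card #2 = 42 − w.

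| Visit 3 on | Days with thermometer | Days without | Overlap with Card #1 | Under Card #2 |
|---|---|---|---|---|
| Day 6 | 37 (88.1%) | 5 | 1 | 36 |
| Day 7 | 36 (85.7%) | 6 | 1 | 35 |
| Day 8 | 35 (83.3%) | 7 | 1 | 34 |

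**Share of the solicited period on a card meant for it.** Card #1 covers 7 of the 42 days in item 2 (7/42 = 16.7%) and 7 of the 360 days in Section 13.2.1 (7/360 = 1.9%).

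**Scheduled week-1 vital signs.** Days 1-7 less Days 3 and 7 leaves Days 1, 2, 4, 5 and 6: 5 of 7 days with no protocol-scheduled reading. The protocol does not say that vital signs include temperature; the count assumes they do.

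**Where the participant is in week 1.** The synopsis gives in-hospital surveillance for the first 7 days. Section 7.1 and Section 9.1 use telephone contacts on Days 1 and 2. Section 9.1 has those contacts arrange clinic evaluations where needed, and has Visit 1 set an appointment for Day 3. Section 11.1.1 specifies 30 minutes of observation. These do not describe the same setting, so the source of week-1 temperatures cannot be read off the protocol.

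**Grading.** The Section 11.1.4 scale rises from a symptom that does not interfere with activity (Grade 1), through interference and incapacity, to an emergency visit or hospitalization (Grade 4). It contains no numeric limits. A raised temperature or blood pressure with no functional effect and no hospital care is therefore at most Grade 1, whatever its value. The stopping rules in Section 14.3 turn on related SAEs, related severe events, or three related moderate events of one type, so the value alone cannot trigger them.

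**The case against.** The strongest reply is that participants are in hospital for the first week, so a home thermometer issued on Day 7 simply marks discharge. Section 9 lists medical charts as source documents, and Section 11.1.3 lets adverse events be transcribed to the CRF from clinical records. This stands in part. A reader might infer that week-1 fever goes unmeasured, or that a ward reading has no route to the CRF. The documents support neither: a fever charted on the ward and judged an adverse event can reach the CRF. What the reply does not supply is a specified daily temperature, and it depends on an inpatient stay that the Day 1-3 procedures do not fit. It also leaves the stated coverage of weeks 1-6 wrong.

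A second reply is that a later fever would still be written on Card #2, graded, and counted under the stopping rules, which do not separate solicited from unsolicited events. That is right, so it would be too strong to say that later readings have no record. The defect is their classification. The cards themselves are not in the protocol, and their scope is taken from the one-line descriptions.

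A third concerns grading. One might infer that an abnormal vital sign can never be moderate or severe. It can, if it affects function or leads to hospital care. Nor can it be said that footnote 2 commits the trial to numeric limits: it gives none and does not name the guidance, while Section 11.1.4 says its own scale derives from an FDA draft guidance. The two statements may be compatible; the protocol does not show it.

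**Conclusion.** The point holds as an internal contradiction that should be corrected. Self-measurement is impossible on about 6 of the 42 days that item 1 claims to cover (5 to 7 with the visit window). Instrument and solicited-event card coincide on one day, and 35 thermometer days (34 to 36) fall under a card described as unsolicited only. That scope conflicts with item 2, the synopsis, Section 7.1 and Section 13.2.1. If the card sets the label, solicited fever after Day 7 is under-counted and unsolicited fever over-counted; the number of events affected cannot be estimated from the protocol. For the Day 0-7 review, the supportable statement is that no daily temperature record is specified.

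The grading point is separate and smaller: an abnormal value without functional effect stays at Grade 1 or below, and the relation to footnote 2 is left open.

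The conclusion assumes that the card descriptions reflect the cards in use and, for the week-1 count, that vital signs include temperature.

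**What to change.** - Supply the thermometer with Diary Card #1 at Visit 1 (Day 0), or state that the ward reading is transcribed while the participant is an inpatient.
- Put a daily temperature field on Cards #1 and #2, so that the record covers weeks 1-6 as item 1 intends.
- Describe Card #2 as taking solicited as well as unsolicited events, in line with item 2. Then state one solicited period, since the synopsis, Section 7.1 and Section 13.2.1 differ, and align Cards #3 to #5 with it.
- Reconcile the 7-day in-hospital surveillance in the synopsis with the Day 1-3 contacts and appointment in Sections 7.1 and 9.1, and name the source of week-1 temperatures.
- Reconcile the vital-sign sentence in Section 11.1.4 with footnote 2 of the schedule: name the guidance, and state whether the value itself or only its functional effect sets the grade.

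The cost is an earlier hand-out of the same thermometer, one line on two diary cards, and a few sentences of text. Sample size, treatment and visit schedule need no change for the recording fixes.
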